3.2 Exclusion Criteria

Patients who fulfill any of the following criteria will be excluded:

- 3.2.1** Serious concomitant systemic disorders incompatible with the study (at the discretion of the investigator), such as significant cardiac or pulmonary morbidity e.g. congestive heart failure, symptomatic coronary artery disease and cardiac arrhythmias not well controlled with medication) or myocardial infarction within the last 12 months, ongoing infection as manifested by fever.
- 3.2.2** Pregnant or lactating women. Women of childbearing potential with either a positive or no pregnancy test (serum or urine) at baseline. (Postmenopausal woman must have been amenorrheic for at least 12 months to be considered of non-childbearing potential).
- 3.2.3** Any prior chemotherapy, targeted/biologic therapy, or radiation for treatment of the patient's pancreatic tumor.
- 3.2.4** Treatment of other invasive carcinomas within the last five years with greater than 5% risk of recurrence at time of eligibility screening. Carcinoma in-situ and basal cell carcinoma/squamous cell carcinoma of the skin are allowed.
- 3.2.5** Other serious uncontrolled medical conditions that the investigator feels might compromise study participation.
- 3.2.6** Lack of physical integrity of the upper gastrointestinal tract or malabsorption syndrome.
- 3.2.7** Known, existing uncontrolled coagulopathy.

- 3.2.8** Prior systemic fluoropyrimidine therapy (unless given in an adjuvant setting and ted at least 6 months earlier). Prior topical flouropyrimidine use is allowed. Prior unanticipated severe reaction to fluoropyrimidine therapy, or known hypersensitivity to 5-fluorouracil or known DPD deficiency.
- 3.2.9** Participation in any investigational drug study within 4 weeks preceding the start of study treatment.
- 3.2.10** History of uncontrolled seizures, central nervous system disorders or psychiatric disability judged by the investigator to be clinically significant, precluding informed consent, or interfering with compliance or oral drug intake.
- 3.2.11** Major surgery, excluding laparoscopy, within 4 weeks of the start of study treatment, without complete recovery.
- 3.2.12** Patients should not be on cimetidine as it can decrease the clearance of 5-FU. Another H2-blocker or proton pump inhibitor may be substituted before study entry.
- 3.2.13** Participants may not be receiving any other study agents.
- 3.2.14** History of allergic reactions attributed to compounds of similar chemical or biologic composition to 5-fluorouracil, irinotecan, or oxaliplatin.

3.3 Inclusion of Women, Minorities and Other Under Represented Populations

We do not expect the inclusion and exclusion criteria to either over or under represent women, minorities, or under represented populations.

4 REGISTRATION PROCEDURES

4.1 General Guidelines for DF/HCC and DF/PCC Institutions

Institutions will register eligible participants with the ODQ in the Clinical Trials

Management System (CTMS) OnCore. Registration must occur prior to the initiation of therapy. Any participant not registered to the protocol before treatment

begins will be considered ineligible and registration will be denied.

A member of the study team will confirm eligibility criteria and complete the protocol-specific eligibility checklist.

Following registration, participants may begin protocol treatment. Issues that

would cause treatment delays should be discussed with the Principal Investigator. If

a participant does not receive protocol therapy following registration, the participant's

protocol status must be changed. Registration cancellations must be made in OnCore

as soon as possible.

4.2 Registration Process for DF/HCC and DF/PCC Institutions

DF/HCC Standard Operating Procedure for Human Subject Research titled *Subject*

Protocol Registration (SOP #: REGIST-101) must be followed.

5 TREATMENT PLAN

Treatment will be administered on an outpatient basis and will include administration of the FOLFIRINOX regimen followed by Proton or Photon Radiation Therapy with capecitabine. Expected toxicities and potential risks as well as dose modifications for FOLFIRINOX and Radiation are described in Section 6 (Expected Toxicities and Dosing Delays/Dose Modification). No investigational or commercial agents or therapies other than those described below may be administered with the intent to treat the participant's malignancy.

5.1 Pre-Treatment Criteria

Prior to study enrollment patients must undergo the following evaluations:

Within 42 days of enrollment: Chest CT and Abdominal-pelvic CT (or MRI). If available, Paraffin-embedded block or ten unstained slides will be used from the untreated biopsy specimen obtained at the time of upper endoscopy or initial diagnostic biopsy for SNaPSHOT analysis.

Within 7 days of enrollment: Physical exam, Lab studies (CBC with diff, Na, K, BUN, Cr, Glucose, Calcium, Albumin, AST, ALT, Total bilirubin, Alkaline phosphatase, CA19-9, CEA, and a urine or serum HCG for women of childbearing potential).

If a patient has undergone biliary stent placement, the following eligibility guidelines will apply. If ALT and AST are elevated beyond 2.5 x the upper limit of normal at time of study enrollment, but demonstrate two consecutive down-trending values, the patient should begin treatment without Irinotecan, or with dose-reduced Irinotecan if clinically indicated. The agents 5-FU and Oxaliplatin may be given during Cycle 1 with Irinotecan incorporated as laboratory values permit. If total bilirubin is elevated above 2.0 mg/dl at time of enrollment, the patient may begin Cycle 1 with full dose 5-FU and Oxaliplatin, with Irinotecan incorporated as laboratory values permit. If total bilirubin is elevated between the upper limit of normal and 2.0 mg/dl at time of enrollment, the patient may receive full dose 5-FU and Oxaliplatin, with dose-reduced Irinotecan. Irinotecan may be increased to full dose in the first or second cycle if laboratory values permit.

Evaluations obtained to confirm study eligibility may be used as pre-treatment evaluations provided they are done within the above timeframes.

5.2 Agent Administration

Study participants will receive up to 8 cycles of FOLFIRINOX as indicated in the study schema. All treatments shall be administered according to institutional standard of care.

5.2.1 5-Fluorouracil: 5-FU will be administered at a dose of 400 mg/m² push per institutional standard on day one, followed by a 1200 mg/M²/d by continuous

infusion via an ambulatory infusion pump for the subsequent two days. 5-Fluorouracil is not a vesicant or irritant. Initial dose of 5-FU may be reduced if necessary; then gradually increased to full dose if tolerated. All dose adjustments are to be made at the discretion of the treating medical oncologist.

5.2.2 Oxaliplatin: Oxaliplatin will be administered as a dose of 85 mg/m² by intravenous infusion over 120 minutes. Infusion time may be prolonged (up to 6 hours) in patients experiencing pharyngolaryngeal dysesthesia. Oxaliplatin is unstable in the presence of chloride or alkaline solutions. Do NOT mix or administer oxaliplatin with saline or other chloride-containing solutions. Do NOT administer other drugs or solutions in the same infusion line. Flush IV lines/catheters with Dextrose 5% in Water both before and after oxaliplatin administration. Initial dose of Oxaliplatin may be reduced if necessary; then gradually increased to full dose if tolerated. All dose adjustments are to be made at the discretion of the treating medical oncologist.

5.2.3 Leucovorin: Leucovorin (400 mg/m²) will be diluted with 5% dextrose and administered concurrently (in separate containers using a Y-type administration set) by IV infusion over 2 hours.

5.2.4 Irinotecan: In this study irinotecan will be administered as a dose of 180 mg/m² by intravenous infusion over 90 minutes. Initial dose of Irinotecan may be reduced if necessary; then gradually increased to full dose if tolerated. All dose adjustments are to be made at the discretion of the treating medical oncologist.

5.2.5 Capecitabine: The dose of capecitabine will be given orally 825 mg/m² BID (total 1650 mg/m² per day) for a total of 10 days M-F during the week of, and the week after, proton beam radiation; or the two weeks of photon radiation. The dose of capecitabine will be fixed unless there are dose level reductions. The daily dose will be administered in two divided doses approximately 12 hours apart. The medication should be given

within 30 minutes after the end of a meal or snack and swallowed with about 8 oz. of water. The dose of capecitabine will be calculated on the basis of milligrams of drug per square meter of body surface area (BSA). Doses will be rounded to the nearest multiple of whole tablets. Capecitabine tablets are either 150 or 500 mg in size, so the dose given will be rounded to the nearest 150 mg tablet. The BSA will be rounded to the nearest tenth and the investigator will prescribe capecitabine according to the following chart. The dose of capecitabine will not exceed 2000mg po bid. All dose adjustments will be at the discretion of the treating investigator.

Table 1: Capecitabine Dosing

BSA (m ²)	Dose BID (Total mg per dose)	500 mg tabs	150 mg tabs
1.0	800	1	2
1.1	1000	2	0
1.2	1000	2	0
1.3	1000	2	0
1.4	1150	2	1
1.5	1300	2	2
1.6	1300	2	2
1.7	1500	3	0
1.8	1500	3	0
1.9	1500	3	0
			1
2.0	1650	3	
2.1	1800	3	2
2.2	1800	3	2
2.3	2000	4	0
2.4	2000	4	0
2.5	2000	4	0

If vomiting occurs around the time of capecitabine ingestion or if doses of capecitabine are missed, additional (“make-up”) doses of capecitabine should not be administered. A drug diary will be provided to document appropriate administration.

5.2.6 Radiation Therapy

5.2.6.1 Simulation and Planning

Tumor volume will be defined on the basis of CT and MRI imaging findings and operative notes and findings. The primary tumor and any clinically enlarged lymph nodes will be treated with a margin of 2 cm to include peripancreatic nodes. The porta hepatis, celiac axis, superior mesenteric artery (SMA) root, and the pancreaticoduodenal nodes will also be treated.

Total dose will be prescribed to the 95 to 100% isodose line based on coverage and will be 25 CGE protons in 5 fractions (5 Gy/day) or 30 Gy photons in 10 fractions (3 Gy/day) with multifield techniques. A dose painted boost to involved vasculature is permitted to a total dose of 30 Gy. Radiation treatment assignment will be based on resource availability at the time of radiation planning.

Patients will be simulated supine. Intravenous and oral contrast will be administered per standard department protocol. 4-D planning CT will be obtained for treatment planning to ascertain the extent of tumor motion.

The Gross Tumor Volume (GTV) is defined as the gross primary tumor and any lymph nodes enlarged over 1 cm during simulation using contrast given during CT or MRI. The clinical target volume (CTV) will also include the following at-risk nodal basins: porta hepatis, celiac axis, superior mesenteric artery, and pancreaticoduodenal nodes as defined by the inner-third of the duodenum. Planning target volume (PTV): PTV will be customized based on 4D CT scan. Generally 0.5 cm expansion will be used, except for superiorly/inferiorly 0.7 cm will be used.

Computerized dosimetry is required if more than two fields are used. All fields must be simulated using a machine that duplicates the geometry of the actual treatment machine. Patient contours and isodose plots are required. Isodose plots must account for the effect of all treated fields, including any blocking used.

5.2.6.2 Treatment

All radiation treatment will be given with the patient at the Francis H. Burr Proton Therapy Center or the Clark Center for Radiation Oncology at MGH. Film or digital images will be taken prior to each treatment in accordance with the Department of Radiation Oncology’s standard practice for all patients. These images are used to verify the position of the patient and the aperture. These digital images are permanently stored electronically for each patient.

Radiation treatment must start on a Monday-Wednesday. If the proton center is unexpectedly not functioning for 1-2 days, these fractions may be made up the following week. However, if the proton center is not functioning longer than 2 days, patients may receive photon radiation for the remaining fractions. If radiation therapy start is delayed beyond 4 weeks after completion of FOLFIRINOX due to toxicity, the patient will proceed to radiation therapy on study at the discretion of the treating investigator.

5.2.6.3 Normal tissue volume and dose considerations

Normal tissue guidelines are as outlined below.

Table 2: Planning Goals - Normal tissue constraints

Organ	Normalized Total Dose (2 Gy equivalents)	Threshold Dose-5 fraction schedule (CGE)	% Above threshold
Liver	23.0 Gy ₂	17.5	30%
Kidney	14.8 Gy ₃	13	30%
Spinal Cord	40.6 Gy ₂	24	0%
Stomach	38 Gy ₁₀	7	10%

Assumed α/β in subscripts

- * If possible - Stomach dose threshold is to prevent nausea, an acute effect. No established guidelines exist. However, in the preliminary MGH IMRT experience, the above dose threshold is associated with ~ 10% rate of ANY anti-emetic use. The daily NTD of the conventional schedule is 1.36 Gy. This means that that the threshold dose (NTD) for a five fraction schedule is 6.8 Gy (2 Gy equivalents) and correlates with the listed dose threshold.

Treatment planning should be adjusted for decreased renal function based on an elevated serum creatinine, a history of unilateral or bilateral renal disease, and abnormalities in baseline laboratory or radiographic studies. Additional studies to assess renal function will be performed as needed. For protons, passively scattered protons and pencil beam protons are both permitted. For photons, 3D photons and IMRT are both permitted.

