2.2.6 Equivalence of Proposed Radiation Schedules

2.2.6.1 Clinical Efficacy

The role of neoadjuvant and adjuvant radiation therapy for resectable pancreatic cancer is to improve locoregional control by sterilizing microscopic disease that may not be removed with surgery. Hence, there may not be a clear benefit to higher doses of radiation therapy in this setting. The table below shows the biological and normalized equivalence among a conventional radiation schedule and the two proposed dose arms in this study.

Efficacy Comparison of Conventional and proposed radiation schedules:

Schedule	Dose per fraction	# Tx	Total Dose	*B.E.D (Gy) (no time correction)	**N.T.D (Gy) (no time correction)	*B.E.D. (Gy) (time correction)	**N.T.D. (Gy) (time correction)
Conventional	1.8 Gy	28	50.4	50.4	59.5	46.8	39
MDACC	3 Gy	10	30	39	32.5	39	32.5
MGH Proton	5 Gy (RBE)	5	25	37.5	31.3	37.5	31.3

*B.E.D. – Biologically equivalent dose

**N.T.D. – Normalized Total Dose, or equivalent physical dose if delivered in 2 Gy fractions.

RBE – Relative Biological Equivalent, assuming a Relative Biological Effectiveness of 1.1.

No repopulation (no time correction):

$$B.E.D = nd(1+d/\alpha/\beta)$$

With repopulation (time correction):

$$B.E.D = nd(1+d/\alpha/\beta) - (T-T_k)(\ln 2/(\alpha \tilde{T}_{pot}))$$

Where:

n = number of fractions

d = dose per fraction

nd = total dose

T = total time of treatment in days

T_k = time after start of treatment repopulation begins

T_{pot} = potential doubling time

Assuming:

$$\alpha/\beta = 10$$

$\alpha = 0.35$ T = assuming treatment starts on a Monday with no breaks during treatment

$$T_k = 28 \text{ d}$$

$$T_{pot} = 5 \text{ days}$$

$$N.T.D. = B.E.D. / (1+2/\alpha/\beta)$$

As demonstrated in the above Table, the reason for similar clinical outcomes between a conventional schedule and the MD Anderson 30 Gy short course may be due to both the larger fraction size and shorter treatment time. Similarly, in looking at the 25 Gy schedule, one would expect very similar clinical efficacy.

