2.2.6.2 Clinical Toxicity

With alteration of a radiation schedule, there is always concern that the toxicity of treatment may increase. However, when investigators at MD Anderson moved from a conventional schedule to a short course, the clinical tolerability in fact improved. Furthermore, with larger fraction sizes, there is also a concern for increased late effects. Using linear-quadratic formulation, the risk for late effects appears to be lower for late effects than with a conventional schedule.

Late Effect Comparison of conventional, MD Anderson Short Course, and proposed schedule ($\alpha/\beta = 3$):

Schedule	Dose/fraction	# Tx	Total Dose	B.E.D (Gy)	**N.T.D. (Gy)
Conventional	1.8 Gy	28	50.4	80.6	48.4
MDACC	3 Gy	10	30	60	36
MGH Proton	5 CGE	5	25	66.7	40

In a randomized trial for low-lying rectal cancers comparing conventional fraction with 5 Gy x 5, an analysis of perioperative complications was also performed²⁸. There were no differences in the rates of complications or in severe complications. These results suggest that there should not be an increase in surgical complications with this either of the proposed radiation schedules in this study.

Recommended dose limits for both acute and late effects can be adjusted for the accelerated schedule. However, the fewer number of fractions render the constraints significantly more stringent.

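### Table 2: the liver's normalized dose, 5-fraction threshold and alpha/beta do not agree under the protocol's own formula

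*Combined protocol and SAP*

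**What the plan says.** Section 5.2.6.3, Table 2, lists normal-tissue planning goals for four organs. Each row gives a normalized total dose in 2-Gy equivalents with a subscript, a threshold dose in CGE for the 5-fraction schedule, and the percentage allowed above that threshold. The liver row reads "Liver 23.0 Gy ₂ 17.5 30" percent. The note below the table explains the subscripts: "Assumed α/β in subscripts". The other rows are:

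- Kidney: 14.8 Gy, subscript 3, 13 CGE.
- Spinal cord: 40.6 Gy, subscript 2, 24 CGE.
- Stomach: 38 Gy, subscript 10, 7 CGE.

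Only the stomach row has an explanatory footnote. It scales a daily normalized dose of 1.36 Gy to five fractions and concludes that "the threshold dose (NTD) for a five fraction schedule is 6.8 Gy (2 Gy equivalents) and correlates with the listed dose threshold".

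Section 2.2.6.1 defines the normalized total dose (NTD) as "Normalized Total Dose, or equivalent physical dose if delivered in 2 Gy fractions" and gives the formulas for it and for the biologically equivalent dose (BED). Section 2.2.6.2 applies the same formulas to late effects at alpha/beta 3 and says that dose limits can be adjusted for the accelerated schedule.

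**The concern.** The first two dose columns of Table 2 should be two expressions of one limit, linked by the stated alpha/beta and five fractions. In the liver row they are not: the 5-fraction threshold is higher than the normalized dose allows at the printed alpha/beta.

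These are the only liver limits in the protocol. The treated volume includes the porta hepatis (section 5.2.6.1), and liver damage is a listed, though much less common, radiation toxicity (section 6.1.2). If 23.0 Gy at alpha/beta 2 is the intended goal, a proton plan built to 17.5 CGE lets more dose through than intended.

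The table also gives no threshold for the 10-fraction photon schedule, so a photon planner who uses it would have to convert from the normalized dose. The two modalities would then be held to different liver limits (23.0 Gy against 24.1 Gy equivalent), although section 5.2.6.1 assigns modality by resource availability.

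**Working it through.** **Formula (section 2.2.6.1, no repopulation term).** With n fractions of d:

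- BED = n·d·(1 + d/(α/β))
- NTD = BED / (1 + 2/(α/β))

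**Check on the protocol's own figures.** The late-effect table in section 2.2.6.2 (α/β = 3) is reproduced in full:

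- 28 × 1.8 Gy: BED 80.6, NTD 48.4
- 10 × 3 Gy: BED 60, NTD 36
- 5 × 5 CGE: BED 66.7, NTD 40

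**Liver, threshold to normalized dose.** n = 5, d = 17.5/5 = 3.5, α/β = 2:

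- BED = 17.5 × (1 + 3.5/2) = 48.125
- NTD = 48.125 / (1 + 2/2) = 24.06 Gy, against 23.0 printed (+1.06 Gy, +4.6%)

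**Liver, normalized dose to threshold.** BED = 23.0 × 2 = 46. Solving 5d(1 + d/2) = 46 gives d = 3.405, so the total is 17.02 CGE, against 17.5 printed (a difference of 0.48 CGE).

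**Rounding.** Totals that round to 17.5 at the nearest 0.5 CGE run from 17.25 to 17.75. At α/β = 2 they give 23.50 to 24.63 Gy, which excludes 23.0. In the other direction, 22.95 to 23.05 Gy gives 17.00 to 17.05 CGE, which would print as 17 or 17.0.

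**Other rows, normalized dose converted to a 5-fraction total.**

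| Organ | NTD (Gy) | α/β | Computed (CGE) | Printed (CGE) |
|---|---|---|---|---|
| Kidney | 14.8 | 3 | 13.15 | 13 |
| Spinal cord | 40.6 | 2 | 23.93 | 24 |
| Stomach (footnote) | 6.8 | 10 | 7.14 | 7 |
| Liver | 23.0 | 2 | 17.02 | 17.5 |

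The stomach's 38 Gy belongs to the conventional 28-fraction schedule: 38/28 = 1.36 Gy per day, and 5 × 1.36 = 6.8 Gy.

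**Other explanations tried for 17.5 CGE at α/β = 2.** Dividing or multiplying by the relative biological effectiveness of 1.1 gives 20.6 or 28.2 Gy. Using 10 fractions gives 16.4 Gy. None gives 23.0.

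**What α/β would reconcile the two doses?** Setting 17.5(1 + 3.5/x) = 23(1 + 2/x) gives x = (61.25 − 46)/(23 − 17.5) = 2.77. At α/β = 3, 23.0 Gy converts to 17.62 CGE, and the range 17.25 to 17.75 gives 22.25 to 23.25 Gy, which includes 23.0. A subscript of 3 would therefore reconcile the row at half-CGE rounding.

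**The case against.** **Direct conversion is an inference.** Table 2 does not say that the threshold column was computed from the normalized-dose column, and the stomach's 38 Gy plainly does not convert to 7 CGE. That is true as far as it goes. But the protocol speaks of adjusting limits for the accelerated schedule, the kidney and cord rows do convert, and the stomach exception has its own explanation. The liver row is the only one neither reproduced nor explained.

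**The other rows are approximate too.** Converted back, 13 CGE gives 14.56 against 14.8 Gy (−1.6%), 7 CGE gives 6.65 against 6.8 Gy (−2.2%), and 24 CGE gives 40.8 against 40.6 Gy (+0.5%). Those gaps are what rounding to a whole CGE produces. The liver's +4.6% is not, and its threshold is printed to a half CGE, which leaves less room for rounding.

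**The subscript may be misprinted, or misread from the PDF.** This cannot be excluded from the text available. The cord's 2 and the kidney's 3 both reproduce, but that does not prove the liver's. It is why the source has to be checked before anything is changed for good.

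**An interim 17.0 CGE goes beyond the evidence.** It is a precaution, not a correction. A plan with no more than 30% above 17.0 CGE also has no more than 30% above 17.5 CGE, so it meets the goal on either reading.

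**The consequence is very small.** This stands. These are planning goals that tolerate 30% above threshold, and nothing in section 14 depends on them.

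**Conclusion.** The inconsistency is real: at least one of the three liver entries is wrong under the protocol's formula. The size is at most 0.48 CGE (about 3%) in the 5-fraction threshold, or 1.06 Gy (4.6%) in the normalized dose. It is zero in dose terms if only the subscript is wrong. The conclusion assumes that the two columns express the same limit through the section 2.2.6.1 formula, as the other rows indicate, and that the printed characters were read correctly.

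Which entry is wrong cannot be settled from the documents. There is a hint towards the threshold: if the liver limit began as 30 Gy in 28 fractions, a figure the protocol does not state, α/β = 2 gives 23.04 Gy while α/β = 3 gives 24.4 Gy. That rests on an assumed starting dose and carries no weight here.

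This is a minor correction to a treatment-planning table. It does not affect eligibility, the prescribed dose, the R0 endpoint or the sample size.

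**What to change.** Check the original liver calculation and change the one entry that is wrong:

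1. If 23.0 Gy at alpha/beta 2 was intended, set the 5-fraction threshold to 17.0 CGE.
2. If 17.5 CGE at alpha/beta 2 was intended, restate the normalized dose as 24.1 Gy.
3. If alpha/beta 3 was used, change the subscript to 3 and leave both doses.

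Until the row is reconciled, plan to 17.0 CGE. The cost is one table cell or one subscript, and in the interim a liver goal 0.5 CGE tighter than printed.
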